## Statistical Analysis Plan

Imputation of missing FEV1 measurements by means of BOCF is a reasonable assumption in studies of adult subjects with cystic fibrosis, as those subjects who discontinue will no longer receive treatment and are thus likely to promptly return to their baseline lung function. Imputation by BOCF specifically inhibits any possible prolongation of an observed early treatment benefit implicitly conferred by a mixed model. Considering the higher drop-out rate observed with the experimental treatment compared to control in previous studies (DPM-CF-301 and DPM-CF-302), BOCF is not likely to favour the mannitol arm.

The primary analysis will target the de facto estimand assessing the effect of a treatment policy (Estimand 1 in Mallinckrodt ) by:

- Including all available on-treatment and off-treatment period data.
- Handling missing data based on a clinically reasonable assumption not biased in favor of the mannitol arm.

### 8.1.2. Sensitivity Analyses of the Primary Endpoint

To elicit insights into the effect of imputation via the planned BOCF+IUDR framework, the following sensitivity analyses of the primary endpoint will be conducted:

- Sensitivity Analysis 1: Pattern Mixture Model.
- Sensitivity Analysis 2: Tipping Point Analysis.
- Sensitivity Analysis 3: MMRM without imputation.
- Sensitivity Analysis 4: Responder Analysis.

As for the primary analysis, these sensitivity analyses target the de facto estimand assessing the effect of a treatment policy. These analyses will include all available on-treatment and off-treatment period data, regardless of adherence to or discontinuation of trial medication.

Planned approaches for handling missing data in Sensitivity analyses 1, 2, and 4 are not likely to favor the experimental arm (for more details see specific sections below.)

In the first 3 analyses, the mean absolute change from baseline FEV1 (L) over 26 weeks (including assessments at Weeks 6, 14 and 26) and at each post-baseline visit will be compared between the two treatment groups. For the responder analysis, the comparison between treatment groups will be performed at Week 26 (however subjects who withdraw from the trial earlier are assumed to be non-responders).

#### Sensitivity Analysis 1: Pattern Mixture Model

A potential disadvantage of employing a single imputation method such as BOCF is the risk of underestimating the variability. To assess the possible impact of this effect,

Pharmaxis Ltd

DPM-CF-303

Final v1.0

## Statistical Analysis Plan

missing FEV1 values at post-baseline visits will be imputed using multiple imputation (MI) from the distribution of baseline values, using the method of Ratitch et al for pattern imputation based on reasons for dropout.

This approach is in line with the one defined for the primary endpoint analysis, where subjects withdrawing from the trial for AE, death, physician decision or lack of efficacy are considered to stop benefiting from the trial medication and return to their baseline status (i.e. BOCF approach; see GRP2 imputation model below), while for subjects withdrawing from the trial for other reasons, it is assumed that they would have continued to benefit from the trial medication in line with subjects completing the trial (see GRP4 and GRP6 imputation models below).

In a preliminary step, imputation based on the missing at random (MAR) assumption will be performed using the joint modeling approach in order to obtain monotone missing data patterns. The imputation model will include the following variables: treatment group, rhDNase use, pooled country, FEV1 (L) from Visit 0 to Visit 4.

Then, a regression-based imputation will be performed for the remaining missing FEV1 values. The strategy for imputation will be based on the definition of the following groups of observed data and patterns of missingness:

(GRP1) Subjects from both treatment groups with non-missing baseline FEV1 values

(GRP2) Subjects from both treatment groups who withdraw from the trial due to AE, death, physician decision, or lack of efficacy

(GRP3) Subjects in the control group who completed the trial

(GRP4) Subjects in the control group who withdraw from the trial because of other reasons

(GRP5) Subjects in the mannitol group who completed the trial

(GRP6) Subjects in the mannitol group who withdraw from the trial because of other reasons

Imputation will be performed:

- In pattern (GRP2) using a model for baseline FEV1 including rhDNase use, pooled country and FEV1 (L) at Visit 0, estimated on the (GRP1) group.
- In pattern (GRP4) using a model including rhDNase use, pooled country, FEV1 (L) from Visit 0 to Visit 4, estimated on the (GRP3) group.

Pharmaxis Ltd

DPM-CF-303

Final v1.0

## Statistical Analysis Plan

- In pattern (GRP6) using the same model described in the previous bullet point, estimated on the (GRP5) group.

One thousand imputations will be performed and for each imputed dataset the analysis of the change from baseline FEV1 (L) over 26 weeks (the mean of values at Weeks 6, 14 and 26) will be based on an ANCOVA model including the following variables: treatment group, rhDNase use, pooled country, baseline FEV1 and disease severity (percent predicted FEV1 at baseline). Also the changes at each post-baseline visit will be analyzed using the same ANCOVA model. Estimates from the models will be then combined using Rubin's rule.

### Sensitivity Analysis 2: Tipping Point Analysis

If a significant difference between treatments is found in the primary analysis, a tipping point analysis will be performed.

The hypothesis behind this approach is that subjects withdrawing from the trial will have a worse outcome (FEV1) compared to subjects completing the trial by a certain amount of mL, with penalties applied to the missing information varying between the two treatment arms. This analysis will explore the influence of missingness, providing evidence of the 'tipping' point where there is no longer evidence of a treatment effect on improvement from baseline of FEV1.

In a preliminary step, imputation based on the missing at random (MAR) assumption will be performed in order to obtain monotone missing data patterns as above described for Sensitivity Analysis 1.

Then, a regression-based imputation will be performed for the remaining missing FEV1 values (regardless of the reason for withdrawal from the trial). The imputation model will include the following variables: treatment group, rhDNase use, pooled country, FEV1 (L) from Visit 0 to Visit 4. Subjects who withdraw from the trial will then have their unobserved post-baseline FEV1 values worsened by an amount  $\delta$  compared to the observed FEV1 of subjects who continue. The analysis will find a tipping point in the spectrum of assumptions on the magnitude of  $\delta$  in the mannitol group at which conclusions change from being favorable to mannitol to being inconclusive (non-statistically significant mean difference between treatments over 26 weeks). The tipping point will be determined in the scenarios described in Table 5:

## Statistical Analysis Plan

**Table 5:  $\delta$ -adjustments to Identify the Tipping Point**

$\delta$ -adjustment in the control group	$\delta$ -adjustment in the mannitol group (in order to identify the tipping point)
0	-0.020, -0.040, -0.060, ... L
-0.020 L	-0.020, -0.040, -0.060, -0.080, ... L
-0.040 L	-0.040, -0.060, -0.080, -0.100, ... L
-0.060 L	-0.060, -0.080, -0.100, -0.120, ... L
-0.080 L	-0.080, -0.100, -0.120, -0.140, ... L
-0.100 L	-0.100, -0.120, -0.140, -0.160, ... L

where the  $\delta$ -adjustments for the mannitol group will decrease by 20 mL up to reaching the non-statistical significance of the treatment comparison.

In each scenario one thousand imputations will be performed and the analysis of the change from baseline FEV1 (L) over 26 weeks will be conducted using an ANCOVA model in line with the specification made for Sensitivity Analysis 1.

### Sensitivity Analysis 3: MMRM Without BOCF Imputation

The same MMRM as for the primary analysis will be used without performing any imputation of post-baseline measurements.

This analysis is based on a MAR assumption on missing data, i.e. on the assumption that unobserved outcomes of subjects who withdraw from the trial do not systematically differ from observed outcomes of subjects who remained in the trial.

[figure not shown]
### Sensitivity Analysis 4: Responder Analysis

A subject will be defined as:

- A responder if they have a change from baseline FEV1 (L)  $\geq$  threshold at Week 26.
- A non-responder if they have a change from baseline FEV1 (L)  $<$  threshold at Week 26 or missing change from baseline FEV1 at Week 26.

The hypothesis is that subjects withdrawing from the trial are not expected to benefit from the treatment, and so are considered as 'Non-responders'.

Three different thresholds will be considered: 0.100, 0.075 and 0.050 L.

## Statistical Analysis Plan

Considering the higher drop-out rate observed with the experimental treatment compared to control in previous studies (DPM-CF-301 and DPM-CF-302), responder analysis is not likely to favor the experimental arm.

The proportion of responders will be summarized and compared between treatment groups using logistic regression. The model will include the same covariates as specified in the primary analysis. The treatment group effect odds ratio and its 95% CI and p-value will be presented.

[Redacted text block]

### 8.1.3. Supportive Analyses of the Primary Endpoint

#### 8.1.3.1. Supportive Analyses of the Primary Endpoint – PP Set

##### Supportive Analysis 1: MMRM with BOCF+IUDR Imputation, PP set

Same statistical model as for the primary analysis (Section 8.1.1), but considering the PP set. This will provide an extra robustness check on the primary results from the ITT set. Any measurements excluded from the PP analysis at the BDRM will be treated as missing data but will not be included in the imputation process.

#### 8.1.3.2. Supportive Analyses of the Primary Endpoint – Results at Each Visit

##### Supportive Analysis 2: MMRM with BOCF+IUDR Imputation, at Week 6/Week 14/Week 26

Using the same statistical model as for the primary analysis (Section 8.1.1), results will be presented also for the treatment group effect at each of the 3 post-baseline visits.

[Redacted text block]

## Statistical Analysis Plan

### 8.1.3.3. Supportive Analyses of the Primary Endpoint – Additional FEV1 Evaluations

In addition to the evaluation of the mean absolute change from baseline FEV1 (L) over 26 weeks, the following supportive analyses based on the FEV1 parameter will be analyzed:

**Supportive Analysis 3: Absolute Change from Baseline Percent Predicted FEV1 (%) Over 26 Weeks**

**Supportive Analysis 4: Relative Change from Baseline FEV1 (L) Over 26 Weeks**

**Supportive Analysis 5: Relative Change from Baseline Percent Predicted FEV1 (%) Over 26 Weeks**

Supportive analyses 3, 4 and 5 will follow the same approach as for the primary analysis (Section 8.1.1). For the analyses of percent predicted FEV1, the FEV1 baseline will not be included in the model; the baseline measure of the outcome will be included as baseline percent predicted FEV1 (disease severity).

### 8.1.3.4. Supportive Analyses of the Primary Endpoint – On-treatment Period Data Only

To elicit insights into the effects of including data from subjects after cessation of trial medication (by including these data, the effects of subsequent therapy are attributed to trial medication); the analyses outlined in Section 8.1.1 and 8.1.2 will be repeated for on trial medication data only (i.e. *excluding* data >7 days after trial medication discontinuation).

**Supportive Analysis 6: MMRM with BOCF+IUDR Imputation, On-treatment Period Data**  
Same approach as for the primary analysis (Section 8.1.1), but considering reason for discontinuation from trial medication.

**Supportive Analysis 7: Pattern Mixture Model, On-treatment Period Data**  
Same approach as for Sensitivity Analysis 1 (Section 8.1.2), but considering reason for

## Statistical Analysis Plan

discontinuation from trial medication.

**Supportive Analysis 8: MMRM Without BOCF, On-treatment Period Data**  
Same approach as for Sensitivity Analysis 3 (Section 8.1.2).

### 8.2. HIERACHICAL SECONDARY EFFICACY ENDPOINT(S) AND ANALYSES

All summaries and main analyses outlined below for the hierarchical secondary efficacy endpoints will be repeated by the subgroups of rhDNase use and disease severity (percent predicted FEV1 at baseline) as specified in Section 6.6. For each hierarchical secondary endpoint, the results from the main analysis, the sensitivity analyses, the supportive analyses (where possible i.e. where these are on the same scale as the main analysis results), and the subgroup analyses will be presented in a forest plot for comparison.

#### 8.2.1. Forced Vital Capacity and Other Spirometry Parameters

##### **Descriptive Summaries:**

FVC absolute change from baseline (L) and relative change from baseline (% change) will be summarized by visit using summary statistics for continuous variables. Two summaries will be produced for the ITT set based on actual data and imputed missing data as described for the primary endpoint in Section 8.1.1.

PEF (L/s), FEV1/FVC ratio (%) and FEF25-75 (L/s) absolute change from baseline and relative change from baseline (% change) will also be summarized by visit using summary statistics for continuous variables without imputation of missing data.

##### **Analysis Method:**

The mean absolute change from baseline FVC (L) over 26 weeks (including assessments at Weeks 6, 14, and 26) will be compared between the two treatment groups using the same model as the primary analysis (with a covariate of baseline FVC, rather than baseline FEV1). Missing data will be handled in the same way as for the primary endpoint.

The mean absolute change from baseline FVC (L) will also be presented for the treatment group effect at each of the 3 post-baseline visits.

The other pulmonary function tests (PEF, FEV1/FVC ratio, and FEF25-75) will not be analyzed.

## Statistical Analysis Plan

The criterion for moving to the next endpoint in the analysis will be based on a p-value less than 0.05 for the comparison between the two treatment groups; sensitivity and supportive analyses will not be part of the testing hierarchy.

### 8.2.1.1. Sensitivity Analyses of FVC

#### Sensitivity Analysis 1: Pattern Mixture Model

To assess the possible impact of employing a single imputation method, a pattern mixture model analysis will be conducted, following the same approach as for Sensitivity Analysis 1 (Section 8.1.2) for the primary endpoint (and with a covariate of baseline FVC, rather than baseline FEV1).

#### Sensitivity Analysis 2: MMRM Without BOCF

To elicit insights into the effect of imputation via the planned BOCF+IUDR framework, the main FVC analysis outlined above will be repeated with no imputation of missing post-baseline FVC. This analysis will be performed as described for Sensitivity Analysis 3 of the primary endpoint in Section 8.1.2 (with a covariate of baseline FVC, rather than baseline FEV1).

### 8.2.1.2. Supportive Analysis of FVC

#### 8.2.1.2.1. Supportive Analysis - Results at Each Visit

[figure not shown]
**Supportive Analysis: MMRM with BOCF+IUDR Imputation, at Week 6/Week 14/Week 26**

Least squares means (LS means) and mean treatment group difference, SE, 95% CIs, and p-value will be presented not only for the treatment groups averaged across the trial, but also for the treatment group effect at each of the 3 post-baseline visits. These results will be obtained by adding specific contrasts to the main model, in line with the approach followed for the primary analysis (Sections 8.1.1 and 8.1.3.2).

### 8.2.2. Time to First Protocol Defined Pulmonary Exacerbation

#### Descriptive Summaries:

Subjects who do not have a PDPE during the trial will be censored at the date of last participation in the trial. The number of subjects with an event and censored will be summarized. Kaplan-Meier product limit estimators of the survivor function (probability of staying event free) will be summarized for 25th percentile, median, and 75th percentile, and their 95% CIs. The plot of Kaplan-Meier estimates for the two treatment groups will also be presented.

## Statistical Analysis Plan

As supportive information the above summaries will be repeated for time to first PE (i.e. all PEs recorded on the CRF with associated antibiotic use, whether or not they met the criteria for a PDPE).

### Analysis Method:

The time (in days) to first PDPE will be analyzed using the Cox's Proportional Hazards model. The model will include the terms treatment group, pooled country, rhDNase use, and number of IV antibiotic treated PEs in year prior to screening (continuous) as factors. The treatment group hazard ratio will be presented with 95% CI and p-value for the treatment group effect.

[Redacted content]

The criterion for moving to the next endpoint in the analysis will be based on a p-value less than 0.05 for the comparison between the two treatment groups; supportive will not be part of the testing hierarchy.

### 8.2.2.1. Supportive Analysis of Time to First Protocol Defined Pulmonary Exacerbation

#### 8.2.2.1.1. Supportive Analysis - All Pulmonary Exacerbations

[figure not shown]
##### Supportive Analysis: Time to First Pulmonary Exacerbation

As supportive information the above analysis will be repeated for time to first PE.

### 8.2.3. Number of Days on Antibiotics Due to Protocol Defined Pulmonary Exacerbation

#### Descriptive Summaries:

The number of days on antibiotics due to PDPE will be summarized using summary statistics for continuous variables (for all subjects in the ITT set and repeated only for

## Statistical Analysis Plan

those with at least one distinct episode of antibiotic usage to treat PDPE) and also for categorical variables using weekly categories (0, 1-7 days, 8-14 days, etc.).

The number of distinct episodes of use of antibiotics due to PDPE will be summarized using summary statistics for categorical variables (e.g. 0, 1-5, etc. or as appropriate to data).

The number of courses of antibiotics due to PDPE will be summarized using summary statistics for categorical variables (no antibiotic use, 1, 2, 3, >3).

As supportive information the above summaries will be repeated for the number of distinct days on antibiotics due to PDPE (excluding overlaps), the number of days on antibiotics due to PE (i.e. all PEs recorded on the CRF with associated antibiotic use, whether or not they met the criteria for a PDPE), and the number of distinct days on antibiotics due to PE (excluding overlaps).

### Analysis Method:

The number of days on antibiotics due to PDPE will be compared between treatment groups using a negative binomial model. [REDACTED] The model will include the categorical effects treatment group, pooled country, rhDNase use, and the continuous covariate number of IV antibiotic treated PEs in year prior to screening. An offset variable of the natural log of follow-up duration (years) will be used in the model to adjust for different lengths of follow-up. The rate ratio will be presented with 95% CI and p-value for the treatment group effect.

[figure not shown]
There will be no imputation of missing data.

[REDACTED]

[REDACTED]

[REDACTED]

## Statistical Analysis Plan

[Redacted text block]

The criterion for moving to the next endpoint in the analysis will be based on a p-value less than 0.05 for the comparison between the two treatment groups; supportive analyses will not be part of the testing hierarchy.

### **8.2.3.1. Supportive Analyses of Number of Days on Antibiotics Due to Protocol Defined Pulmonary Exacerbation**

#### **8.2.3.1.1. Supportive Analysis - Additional Evaluation of the Number of Days on Antibiotics Due to Protocol Defined Pulmonary Exacerbation**

##### **Supportive Analysis 1: Number of Distinct Days on Antibiotics Due to Protocol Defined Pulmonary Exacerbation**

Same approach described in Section 8.2.3 'Analysis Method', but considering the number of distinct days on antibiotics due to PDPE (i.e. excluding overlaps).

#### **8.2.3.1.2. Supportive Analyses - All Pulmonary Exacerbations**

##### **Supportive Analysis 2: Number of Days on Antibiotics Due to Pulmonary Exacerbation**

Same approach described in Section 8.2.3 'Analysis Method', but considering the number of days on antibiotics due to PE (i.e. all PEs recorded on the CRF with associated antibiotic use, whether or not they met the criteria for a PDPE).

##### **Supportive Analysis 3: Number of Distinct Days on Antibiotics Due to Pulmonary Exacerbation**

Same approach described in Section 8.2.3 'Analysis Method', but considering the number of distinct days on antibiotics due to PE (i.e. excluding overlaps and considering all PEs recorded on the CRF with associated antibiotic use, whether or not they met the criteria for a PDPE).

## Statistical Analysis Plan

### 8.2.4. Number of Days in Hospital Due to Protocol Defined Pulmonary Exacerbation

#### **Descriptive Summaries:**

The number of days in hospital due to PDPE will be summarized using summary statistics for continuous variables (for all subjects in the ITT set and repeated only for those with at least one hospitalization due to PDPE) and also for categorical variables using weekly categories (0, 1-7 days, 8-14 days, etc.). The number of hospitalizations per subject will also be summarized using categories 0, 1, 2, 3, and >3.

As supportive information the above summaries will be repeated for hospitalizations due to PE (i.e. all PEs recorded on the CRF with associated antibiotic use, whether or not they met the criteria for a PDPE).

#### **Analysis Method:**

The number of days in hospital (admissions only) due to PDPE will be compared between treatment groups using a negative binomial model. The model will include the categorical effects treatment group, pooled country, rhDNase use, and the continuous covariate number of IV antibiotic treated PEs in year prior to screening. An offset variable of the natural log of follow-up duration (years) will be used in the model to adjust for different lengths of follow-up. The rate ratio will be presented with 95% CI and p-value for the treatment group effect.

There will be no imputation of missing data.

The criterion for moving to the next endpoint in the analysis will be based on a p-value less than 0.05 for the comparison between the two treatment groups; supportive analyses will not be part of the testing hierarchy.

#### **8.2.4.1. Supportive Analysis of Number of Days in Hospital due to Protocol Defined Pulmonary Exacerbation**

##### **8.2.4.1.1. Supportive Analysis - All Pulmonary Exacerbations**

#### **Supportive Analysis: Number of Days in Hospital Due to Pulmonary Exacerbation**

As supportive information the analysis outlined in Section 8.2.4 'Analysis Method' will be repeated for hospitalizations due to PE (i.e. all PEs recorded on the CRF with associated antibiotic use, whether or not they met the criteria for a PDPE).

## Statistical Analysis Plan

### 8.2.5. Rate of Protocol Defined Pulmonary Exacerbation

#### **Descriptive Summaries:**

Number of PDPEs (0, 1, etc.) and incidence of PDPEs (yes or no) will be summarized using summary statistics for categorical variables.

The number of subjects with PDPEs, the total number of PDPEs, the total follow-up duration (in years), and the overall rate of PDPEs (per person year) will be presented.

As supportive information the above summaries will be repeated for overall rate of PEs (i.e. all PEs recorded on the CRF with associated antibiotic use, whether or not they met the criteria for a PDPE).

#### **Analysis Method:**

[figure not shown]
The rate of PDPEs will be compared between treatment groups using a negative binomial model. The model will include the categorical effects treatment group, pooled country, rhDNase use, and the continuous covariate number of IV antibiotic treated PEs in year prior to screening. An offset variable of the natural log of follow-up duration (years) will be used in the model to adjust for different lengths of follow-up. The rate ratio will be presented with 95% CI and p-value for the treatment group effect.

The criterion for moving to the next endpoint in the analysis will be based on a p-value less than 0.05 for the comparison between the two treatment groups; supportive and sensitivity analyses will not be part of the testing hierarchy.

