#### Primary Analysis Method:

The mean absolute change from baseline FEV1 (L) over 26 weeks (including assessments at Weeks 6, 14 and 26) will be compared between the two treatment groups with a restricted maximum likelihood (REML) based MMRM approach.

The model will include the fixed, categorical effects of treatment group, rhDNase use, pooled country, visit, and treatment group-by-visit interaction, as well as the continuous, fixed covariate of baseline FEV1 and also disease severity (percent predicted FEV1 at baseline). Subject will be included in the model as a random effect. An unstructured (co)variance structure will be used to model the within-subject errors. The Kenward-Roger approximation will be used to estimate denominator degrees of freedom.

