##### Analysis Method:

Proportions will be compared between treatment groups using logistic regression. The model will include the categorical effects pooled country, rhDNase use, and the continuous covariate number of IV antibiotic treated PEs in year prior to screening. The treatment group effect odds ratio, 95% CI, and p-value will be presented.

No imputation of missing data will be performed.

Pharmaxis Ltd

DPM-CF-303

Final v1.0

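### The five exacerbation models leave out baseline percent predicted FEV1; adding it is a small, nearly free gain in efficiency, not the repair of an error

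*SAP*

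**What the plan says.** The five models share one set of baseline adjustments:

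- Time to first PDPE, Cox (SAP 8.2.2): "The model will include the terms treatment group, pooled country, rhDNase use, and number of IV antibiotic treated PEs in year prior to screening".
- Antibiotic days, negative binomial (SAP 8.2.3): "categorical effects treatment group, pooled country, rhDNase use, and the continuous covariate number of IV antibiotic treated PEs in year prior to screening".
- Hospital days, negative binomial (SAP 8.2.4): "effects treatment group, pooled country, rhDNase use, and the continuous covariate number of IV antibiotic treated PEs in year prior to screening".
- PDPE rate, negative binomial (SAP 8.2.5): "The model will include the categorical effects treatment group, pooled country, rhDNase use, and the continuous covariate number of IV antibiotic treated PEs".
- PDPE incidence, logistic (SAP 8.3.1): "The model will include the categorical effects pooled country, rhDNase use, and the continuous covariate number of IV antibiotic treated PEs".

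The lung function and symptom models differ. The primary FEV1 model adds baseline FEV1 "and also disease severity (percent predicted FEV 1 at baseline"). FVC is analyzed "using the same model as the primary analysis (with a covariate of baseline FVC" in place of baseline FEV1), so it keeps the severity term. The expectoration VAS and CFQ-R models (SAP 8.3.2, 8.3.3) name the term explicitly. It is dropped only in the fits by severity subgroup (SAP 6.6).

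Analyses of the hierarchical secondary endpoints "will be repeated by the subgroups of rhDNase use and disease severity", split at 70% predicted (SAP 6.6, 8.2). Randomization is stratified by rhDNase use and country only (Protocol Section 7, SAP 3.6), and country is then pooled to United States versus the rest (SAP 6.5).

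**The concern.** Severity is taken seriously enough to adjust every main mixed model and to define subgroups for four of these five endpoints, yet it adjusts none of the five main exacerbation analyses. SAP Section 11 item 5 added baseline covariates to the mixed models and is silent on the event models.

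Two things are at stake, both modest. If severity predicts exacerbations beyond the prior-year count, some explainable between-subject variation is left unexplained. And because severity is not stratified, a chance difference between arms feeds into the estimated hazard, rate and odds ratios, except for the part the prior-year count absorbs. Four of the endpoints are hierarchical secondaries 2 to 5. Time to first PDPE must reach p<0.05 before the next three can be tested, so even a small amount of power there has some value.

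**Working it through.** **The plan's own figure.** The only sample size calculation is for FEV1: 80 mL difference, SD 230 mL, two-sided 0.05, 90% power (Protocol 10.1.1). Per arm, n = 2 × (1.960 + 1.2816)² × (230/80)² = 2 × 10.507 × 8.266 = 173.7, so 174 per arm and 348 in total, against 350 stated. Power at 175 per arm is 90.2% (normal) or 90.1% (t). It reproduces, but says nothing about the exacerbation models.

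**Inputs for the exacerbation models.** From the documents: 423 randomized (SAP 10), 1:1 allocation, 26 weeks, and eligibility above 40% and below 90% predicted. Assumed, because the documents are silent:

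- control rate 0.2 or 0.4 PDPE per 26 weeks (0.4 or 0.8 per year);
- treatment rate ratio 0.70;
- severity effect of 1.0 to 1.5-fold in rate per 10 points lower percent predicted;
- SD of percent predicted 12 to 14.4 points (a uniform spread over 40 to 90 gives 50/√12 = 14.4);
- a frailty shared by the prior-year count and the on-trial rate, so that the count already carries part of the severity information.

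**Efficiency.** Trials were simulated and fitted with the SAP covariates, without and then with percent predicted FEV1. Gain in effective sample size is the squared ratio of the z-values.

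| Severity effect per 10 points | Rate model | Cox model |
|---|---|---|
| none | about 0% | no real gain possible; −0.5% to +1.9% observed |
| 1.15 | −0.5% to 1% | 0.4% to 2.0% |
| 1.3 | −0.8% to 4% | −0.2% to 2.6% |
| 1.5 | 4% to 5% | not run |

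The logistic model ran from −0.6% to 1.5% over effects of 1.0 to 1.3. Ranges span simulation sets of different size and set-up. The negative entries, and the 1.9% where no gain can exist, come from the smallest set (150 runs per setting) and show its noise. The largest set (875 to 980 usable runs, rate model only) gave about 0%, 0.7%, 2% and 4% down the table. On 423 subjects, 5% is 0.05 × 423 ≈ 21 subjects and 1% is about 4.

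In the 150-run set, power changed as follows:

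- rate model: −0.6 to +1.5 points;
- Cox: 0 to +1.3 points;
- logistic: −2.0 to +0.6 points, the −2.0 being a net 3 trials of 150.

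Each power value carries about 4 points of Monte Carlo error; the paired comparison is less noisy. The median SE moved by at most 0.5% in the rate model. In the Cox and logistic models it rose slightly, by up to 0.6%.

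**Chance imbalance.** The SE of the difference between arms is SD × √(4/423) = SD × 0.0972.

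- SD 12: SE 1.17; 95% limit 1.96 × 1.17 = 2.29 points.
- SD 14.4: SE 1.40; 95% limit 2.74 points.

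The shift in a ratio that carries no severity information is (effect per 10 points)^(imbalance/10):

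- smallest case: 1.1^0.229 = 1.022, log 0.022;
- largest case: 1.3^0.274 = 1.075, log 0.072.

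The simulated SE of the log rate ratio is 0.20 to 0.27. The shift is therefore 0.022/0.27 ≈ 0.1 SE to 0.072/0.20 = 0.36 SE, before the prior-year count absorbs part of it.

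**The case against.** The case for leaving the models alone is strong on several counts.

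- **The choice is prespecified.** Protocol 10.2.7 sets country, rhDNase use and historical exacerbation rate for all five analyses. The SAP carries these over, pooling country and rewording the history term. This stands.
- **The closest baseline analogue is already in.** A PDPE requires intravenous antibiotics, and the prior-year count is of IV-treated exacerbations. Only the increment of lung function beyond that history is at issue, and the documents hold no data on it. This stands, and is why the gain is small.
- **Severity is examined elsewhere.** Baseline severity is tabulated (SAP 7.2), and the hierarchical endpoints are repeated by severity subgroup with forest plots. True, but these displays reveal an imbalance without adjusting for it, and the planned subgroup repeats do not extend to incidence.

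A reader might infer that the omission biases the treatment comparison or invalidates the tests. The documents do not support that: allocation is randomized, and chance imbalance is already reflected in the confidence interval and p-value. A reader might also infer that precision is lost in all five models. In Cox and logistic models a prognostic covariate does not shrink the SE of the conditional ratio; any gain comes from the estimate moving away from the null. Finally, the shifts of 2% to 7.5% computed above apply to a ratio with no severity information at a 95%-extreme imbalance. The planned models include the prior-year count, so those shifts are upper bounds for them.

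**Conclusion.** The omission is real in all five models, and the documents give no reason for it. Its consequence is small: roughly 0% to 5% of effective sample size in the rate model, with the top of that range needing an assumed 1.5-fold rate per 10 points, and about 0% to 3% in the Cox and logistic models. Antibiotic and hospital days were not simulated; they share the covariate set and the model family of the rate analysis. Sensitivity to a 95%-extreme severity imbalance is at most about 0.1 to 0.36 SE for effects of 1.1 to 1.3-fold. If severity has no effect, nothing material is lost.

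All of this rests on the assumed rate, treatment effect, frailty and severity effect. The planned analyses are valid as they stand. This is a free improvement of low severity.

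**What to change.** In SAP 8.2.2, 8.2.3, 8.2.4, 8.2.5 and 8.3.1, and in their sensitivity and supportive versions, add baseline percent predicted FEV1 as a continuous covariate. Cover all five, so that hierarchical endpoints 2 to 5 are adjusted alike. Drop the term in the severity-subgroup fits, as SAP 6.6 already provides. In the multiple-imputation sensitivity analysis of the rate, add it to the imputation model too, so that the two models agree. While editing 8.3.1, list treatment group among the model terms: it is missing from the sentence, although a treatment odds ratio is to be reported.

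Record the change in SAP Section 11 before unblinding. Made afterwards, with a severity imbalance in view, it would look driven by the data. If the sponsor prefers the protocol's covariates, a sentence in Section 11 saying why severity is adjusted for in the mixed models and not here would suffice.

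Cost: one degree of freedom and one sentence per model, and an amendment to a SAP finalized on 23 May 2017. No new data are needed, since baseline is Visit 1, or Visit 0 if that is missing (SAP 6.2.4). The tested models would depart from the protocol's covariate list, and the ratios would be conditional on one more covariate.
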